PROTOCOL TITLE: The Effects of Transcranial Direct Current Stimulation on the Neuronal Mechanisms of Cognitive Control in Schizophrenia

1) Protocol Title

Title: The Effects of Transcranial Direct Current Stimulation on the Neuronal Mechanisms of Cognitive Control in Schizophrenia
Protocol Version Date: 9/23/2019

2) Objectives

The purpose of this study is to better understand the neural correlates of cognitive control (CC) deficits in schizophrenia and determine how these mechanisms can be modulated by transcranial direct current stimulation (tDCS). CC is a critical neurocognitive process that is required for flexible, directed thought and action based on goals and intentions. Identifying and developing paradigms to improve CC is therefore a mental health priority. Current theories of CC postulate that recruitment of the dorsolateral prefrontal cortex (DLPFC) is essential for this process by maintaining high-level information that it can then use to orchestrate patterns of activation in other brain networks to support optimal performance. tDCS is a safe, noninvasive method of modulating regional brain excitability via brief (15-20 m) application of a weak (1-2 mA) current. The goal of the proposed experiments is to combine tDCS with functional magnetic resonance imaging (fMRI) or electroencephalography (EEG) to test the hypotheses that 1) acute tDCS over the DLPFC can improve performance during a CC task (the dot pattern expectancy (DPX) variant of the AX-CPT) in schizophrenia, and 2) acute tDCS over the DLPFC can increase recruitment of the DLPFC during the DPX. Sham stimulation over the DLPFC and acute stimulation over the somatomotor cortex (SMC) will also be performed as control conditions. Effects of tDCS on brain functional connectivity (during CC as well as during the resting state) will also be examined, as well as effects on an episodic memory task. EEG recordings will be incorporated into this study in order to better understand the physiological mechanisms associated with cognitive function, as well as with non-invasive stimulation. The current study will be the first to use fMRI to examine the effects of tDCS on the neuronal mechanisms of CC in schizophrenia, and has potentially important implications for therapeutic development for this treatment refractory yet disabling aspect of the illness.

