“Stimulation Only” or “Stimulation and EEG” electrodes may be used (see electrode chart above). Note, for ease of these experiments, the “Stimulation Only” electrodes will be used in most cases. For these electrodes, sponge electrodes will be moistened (with saline), prior to placement on the subject’s scalp. Alternatively, “Stimulation and EEG” electrodes (PISTIM) will be applied using conductive electrode gel. See chart above for electrode sizes and specification. Up to 8 electrodes may be used at any given time (in addition to external/reference electrodes. See above). Only scalp electrode sites designated on the Starstim cap will be used. The cap only uses standard electrode sites from the 10-20 system.

tDCS stimulation (~25 minutes). During this phase, participants will first receive a few minutes of training on the DPX task and complete a brief practice session. Subjects will also be familiarized with the working memory task (see below). After practice, stimulation (or sham stimulation) will begin.

Following the practice session, subjects will undergo sham with task, DLPFC with task, sham without task, DLPFC without task, or SMC active stimulation. The order of the conditions will be fully counterbalanced across subjects. This experiment involves five tDCS visits, and may include tDCS at any of the designated scalp electrode sites in the Starstim cap. Each stimulation visit will be separated by at least 24-48 hours.

Subjects will receive up to 20 minutes of tDCS stimulation or sham, in addition to a few seconds of ramp up and ramp down time at the beginning and end of each session, using the Starstim device. All subjects will receive up to 2.0 mA for the first 30-60 s of stimulation. Current strength will be ramped down, and then reduced to 0.0-0.1 mA in subjects receiving sham stimulation for the remainder of the session. The active stimulation subjects will continue to receive up to 2.0 mA stimulation. Many participants can feel the onset of the stimulation (which leads to a brief tingling or itching sensation), but people cannot generally feel the continued stimulation beyond one minute. By beginning both the active and sham stimulation conditions with a period of stimulation, we can ensure that participants will not

PROTOCOL TITLE: The Effects of Transcranial Direct Current Stimulation on the Neuronal Mechanisms of Cognitive Control in Schizophrenia

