know if they are receiving active or sham stimulation. The sham conditions serve as an important control, which is similar in procedure and results in similar initial sensations, but does not provide a significant level of stimulation. The SMC stimulation condition is another important, "active" control that controls for the effect of stimulation at a location other than the DLPFC area of interest for which tDCS is hypothesized to have effects on CC.

A sensation questionnaire will be administered at 3 separate time points during stimulation, starting at approximately 5 minutes after the beginning of stimulation, and then approximately every 10 minutes during stimulation. In this assessment, subjects will be asked to report the level of sensation arising from the stimulation on a 10 point scale, with 1 meaning no sensation and 10 meaning mild pain. Stimulation will be terminated immediately if the reported sensation level is 7 or higher at any assessment. Participants—who will be in constant communication with an experimenter—will also be instructed to inform the experimenter if pain is experienced at any other time, which will lead to immediate termination of stimulation. Additionally, the experimenter will monitor the electrodes to ensure that they do not dry out or otherwise cause discomfort.

No-Task Sessions: While subjects are undergoing sham without task or direct current stimulation without task they will rest quietly while seated at a computer desk. The experimenter will be available to chat with the participants and administer the sensation questionnaires as described above. The purpose of the No-Task sessions is to be able to compare the effects of sham/stimulation without task to sham/stimulation with a concurrent task, as previous work has suggested that there may be a benefit to completing a concurrent task during tDCS (see below).

Concurrent Visuospatial N -Back Working Memory Task: While subjects are undergoing sham or direct current stimulation they will concurrently perform a simple "n-back" (three-back) working memory task. This is because tDCS effects on tasks that engage the prefrontal cortex (e.g. the DPX) are enhanced if the stimulation occurs at the same time as either the same task or another task that also engages the prefrontal cortex (i.e. "state-dependent" effects) (Tremblay et al., 2014).

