In the three-back task, subjects will be asked to remember the location of an object presented three objects previously on a computer screen. To register a match, a key on a keypad, keyboard, or mouse will be pressed. No response is required for non-targets.

Wash up: The stimulating electrodes will be removed, cleaned, and disinfected according to the manufacturers instructions. As the electrodes are removed, the experimenter will inspect the skin at and near the electrode sites for redness, irritation, or damage and note if present.

For sessions that include fMRI scans, scanning will begin immediately following wash-up and will last up to 1 hour (Stimulation will only last for 20 minutes). See above for specific imaging procedures.

Mood Assessment (30-90 minutes):

PROTOCOL TITLE: The Effects of Transcranial Direct Current Stimulation on the Neuronal Mechanisms of Cognitive Control in Schizophrenia

After imaging is complete, participants will undergo a relaxation period (~30 minutes) during which the electrodes will be removed and the participants will relax (by sitting quietly or watching a video). Subjects will then take the mood and mental state questionnaire again to make sure that they have no lingering effects of the stimulation. In the unlikely case that a subject still has any lingering effects, the subject will relax for an additional 15 minutes, and then repeat the mood/mental state assessment. This will be repeated until the participant returns to baseline. There are no known reports of lingering effects of tDCS after 90 minutes, so we anticipate that the relaxation period will be complete within 90 minutes in all participants. We will also perform a 48-hour follow-up call or email to ensure that subjects have not experienced any additional adverse effects.

Compensation. Subjects will be compensated \$25 for completing the questionnaires and clinical interview, \$25 for each tDCS session that does not include fMRI or EEG afterwards, \$75 for each tDCS session that is followed by fMRI or EEG, and given a \$50 bonus for completing all sessions of a given modality (EEG or fMRI).

8) Data and/or Specimen Management and Confidentiality

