Normal patient handling procedures are followed to eliminate risks. The subjects will be able to communicate with the investigators at all times. The subject's emotional state and mood will be assessed before and after stimulation; and physical sensation will also be monitored with a questionnaire administered before, during, and after the stimulation procedure (see above for details). The subject can ask to stop the experiment at any time for any reason. Likewise, the experimenter may stop the experiment at any time if the subject reports experiencing any pain or discomfort. When stopping the stimulation, the current will be gradually ramped down using the safe stop mode in order to avoid any unpleasantness or painfulness associated with abruptly aborting stimulation. It is also important to note that individuals may respond differently across tDCS conditions. Therefore, we will monitor all participants closely even when they have completed previous visits with no adverse effects. In the unlikely event that a subject experiences serious side effects or injury due to the experiment, the experimenter will call 911, and these details will be immediately communicated to the IRB. We have identified the following potential risks associated with tDCS and address them in turn:

I. Skin Damage or Irritation: Nitsche et al. (2003) suggest that there may be a slight risk of skin damage or irritation resulting from tDCS stimulation. With the exception of Iyer et al. (2005) who reported transient redness at the stimulating electrode site in two men who had recently shaved their heads, we have encountered no reports of skin damage or irritation in any of the tDCS literature. The possibility of skin damage resulting from electrode heat has also been tested using stimulation parameters comparable to those outlined in this protocol. None of these results have indicated skin damage due to electrode heat. Furthermore, we will be using saline-soaked electrodes, or we will use electrode paste, for our study, which minimizes the possibility of chemical reactions at the electrode-skin

PROTOCOL TITLE: The Effects of Transcranial Direct Current Stimulation on the Neuronal Mechanisms of Cognitive Control in Schizophrenia

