interface and resultant skin damage. The scalps of each subject will be visually inspected immediately before stimulation. Any identified irritation or evidence of recent shaving of the head will postpone or terminate that subject's participation in the study. Subjects will also be asked to remove any jewelry that may come into contact with the electrodes. Subjects will be encouraged at the beginning of the tDCS procedure to report any pain or discomfort that they may encounter throughout the procedure. Any such reports, or evidence of redness or irritation of the scalp, will result in the immediate termination of stimulation. Additionally, subjects will be screened for latex allergies to prevent allergic reactions to the electrodes. If allergic reactions are noted at any time, stimulation will be ceased, and electrodes will be removed. Overall, these methods for prevention of skin damage follow the suggestions of Loo et al. (2011, see above).

To avoid burning the patient, there is a recommended limit of 0.1 mA/cm^2 for DC current applications (per the device manual). For example, using electrodes with a surface area of 35 cm^2 with a current of 1 mA applies a current density of 0.02857 mA/cm^2 . It is possible that subjects may experience pain at lower levels of current, and therefore, we will closely monitor subjects' responses on the questionnaires. To avoid permanent injury of tissue, current density should not be higher than 25 mA/cm^2 at any given electrode site. This limit is far above the limit for thermal effects of the current density. Note that the maximum current in this protocol is 2 mA , and the surface area of the Starstim PISTIM electrodes is 3.14 cm^2 . Other Starstim stimulating electrode options include the SPONSTIM electrodes in either 8 cm^2 or 25 cm^2 . Thus, the maximal current density used in this protocol will range from $0.080 - 0.64 \text{ mA/cm}^2$. Therefore, the maximum current density will always be set below the recommended limit to avoid any skin burning or damage.

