II. Tissue Damage and Discomfort : To minimize any possible tissue damage we have subjects fill out a tDCS sensation questionnaire form throughout the tDCS procedure. This questionnaire allows us to monitor what the subjects are physically feeling at the electrode sites. This will be given at the following time points: 1 minute after start of tDCS, 5 minutes after start of tDCS, and 20 minutes after tDCS. If at any time the subject reports a sensation level of 7 on a 10-point scale, we immediately discontinue the experiment. We will also administer a subjective mood questionnaire before and following experimentation. Any significant changes in answers provided following the experiment will result in further assessment every 15 minutes until subjects return to near baseline state. (also see above "Skin damage or irritation" for further details).

III. Pain: At very strong, focal current density can result in pain. We will be using large electrodes and passing weak electrical current. As previously stated, with protocols similar to ours, most subjects report only mild, transient tingling at the stimulation site. Any subject report of pain resulting from tDCS will result in immediate termination of stimulation.

IV. Alterations in Mood or Affect: There is evidence that tDCS can result in changes in mood and concentration. While no studies have reported negative affect resulting from DC stimulation, several studies have reported improved mood after tDCS. It should be noted that, in these studies, stimulation was applied for significantly longer durations. Studies designed to investigate the safety aspects of non-invasive brain stimulation have reported no significant changes in mood as

PROTOCOL TITLE: The Effects of Transcranial Direct Current Stimulation on the Neuronal Mechanisms of Cognitive Control in Schizophrenia

measured with the VAMS (Visual Analog Mood Scales) and no significant changes in measures of fatigue when comparing stimulation to sham. Therefore, we do not anticipate any changes in mood or affect resulting from our study. To further ensure that subjects are not experiencing alterations in mood or mental state that could potentially debilitate them, we will administer a subjective mood questionnaire before and following experimentation. Any significant changes in answers provided following the experiment will result in further assessment every 15 minutes until subjects return to near baseline state.

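### The three sensation ratings do not fit the 20-minute stimulation limit, and the protocol's sections disagree on rating times and on stopping for non-painful discomfort

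*Protocol*

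**What the plan says.** **Rating times.** The session procedure in Section 7 has the sensation questionnaire administered "at 3 separate time points during stimulation, starting at approximately 5 minutes after the beginning of stimulation, and then approximately every 10 minutes". The same section limits the current: "Subjects will receive up to 20 minutes of tDCS stimulation or sham", apart from a few seconds of ramping, and its wash-up paragraph repeats "Stimulation will only last for 20 minutes". Section 12, under II (Tissue Damage and Discomfort), lists different times for the questionnaire: "1 minute after start of tDCS, 5 minutes after start of tDCS, and 20 minutes after tDCS". The opening paragraph of the risk-minimisation plan in Section 12 describes it a third way, as given before, during and after stimulation.

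**Stopping.** Section 7 requires stimulation to end at once if a rating reaches 7 or more on the 10-point scale, or if the participant reports pain at any other time. The opening paragraph of the plan in Section 12 says: "Likewise, the experimenter may stop the experiment at any time if the subject reports experiencing any pain or discomfort". Section 12, under I (Skin Damage or Irritation), asks participants to "report any pain or discomfort that they may encounter throughout the procedure" and makes any such report a reason to end stimulation immediately. Section 12, under III (Pain), makes any report of pain from the current a compulsory stop. Under II, a rating of 7 leads staff to discontinue the experiment, where Section 7 speaks only of stimulation.

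**The concern.** These are instructions that staff must carry out while current is flowing, and they cannot all be followed. Someone working from Section 7 takes no rating in the first five minutes, although the protocol says the current is felt mainly at onset. Someone working from Section 12 under II takes none between minute 5 and minute 20 or later. The protocol itself names drying electrodes as a cause of skin burns, and drying is a risk of the later part of a session.

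A participant who reports discomfort but not pain may be stopped or continued depending on which paragraph the experimenter has in mind. Periodic questioning and a prompt stop are what the protocol offers as its safeguard against burns, so the rule for applying them should be the same wherever it appears.

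**Working it through.** **Schedule in Section 7.** Inputs: first rating at 5 minutes, spacing 10 minutes, three ratings, stimulation limit 20 minutes. Rating k falls at 5 + 10 × (k − 1):

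- k = 1: 5 minutes, within the limit
- k = 2: 15 minutes, within the limit
- k = 3: 25 minutes, which is 25 − 20 = 5 minutes past the limit

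So 2 of the 3 required ratings fit. To fit three by minute 20 with the first at minute 5, the spacing can be at most (20 − 5) / 2 = 7.5 minutes, a quarter less than the stated 10. To keep a spacing of 10, the first rating would have to be at minute 0 (0, 10, 20). The limit allows shorter sessions, and these fit worse. With 15 minutes of current the second rating falls at the very end, and the third is 25 − 15 = 10 minutes late.

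The stimulation phase headed as about 25 minutes in Section 7 does not supply the missing time. It includes training and practice before the current is switched on.

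**Schedule in Section 12, II.** Ratings at 1 and 5 minutes, and a third that can be read two ways: minute 20 if counted from the start, or about 20 + 20 = 40 if counted from the end. On the second reading the rating could fall inside the scanner at an fMRI visit, because "scanning will begin immediately following wash-up". The two lists share only the 5-minute point. Section 7 has no 1-minute rating, and Section 12 has no 15-minute rating.

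**Stopping rules side by side.**

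| Place | Pain | Discomfort short of pain | Rating of 7 |
|---|---|---|---|
| Section 7, session procedure | must stop stimulation | no stop required unless rated 7 or higher | 7 or higher: must stop stimulation |
| Section 12, plan, opening paragraph | may stop | may stop | not mentioned |
| Section 12, I | must stop stimulation | must stop stimulation | not mentioned |
| Section 12, II | not mentioned | not mentioned | 7: must discontinue the experiment |
| Section 12, III | must stop stimulation | not mentioned | not mentioned |

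In the pain column, three places agree and only the general opening paragraph is looser. In the discomfort column there are three different answers. The review of burn prevention in Section 12 adds a fourth: it lists stopping or adjusting the electrodes as the response to discomfort and says these steps are built into the protocol.

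**What a stop ends.** The opening paragraph of the plan moves from stopping the experiment to stopping the stimulation as if they were one act. Section 7, however, also uses the word experiment for the whole series of five tDCS visits. Under II it could therefore mean the current, the session or the series. Sections 6 and 11 deal separately with ending a person's participation, which makes the last reading less likely but does not settle it.

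**The case against.** The best defence has four parts.

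First, the timings are given as approximate, so staff could compress them. This helps only if the spacing drops from 10 to 7.5 minutes or less, and it cannot explain a different list in Section 12.

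Second, the third time in Section 12 is introduced as part of monitoring throughout the procedure, which favours minute 20 over minute 40. That is fair and makes the later reading less likely, but the list still differs from Section 7.

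Third, the discretionary wording stands in a general introduction that gives both sides the right to stop, and the specific rules follow it. This stands for pain. A reader might infer that stopping for pain is optional, and the documents do not support that: Section 7 and parts I and III of Section 12 all require it, with constant contact with the experimenter as a backstop. For discomfort short of pain the defence fails, because Section 7 is a specific rule too and differs from part I.

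Fourth, a threshold of 7 implies continuing below it, on a scale whose top is only mild pain. That is correct. The lack of an instruction for ratings 2 to 6 is not itself a fault; the conflict arises only because part I of Section 12 would stop for any reported discomfort.

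A reader might also infer that early stops bias the active-versus-sham comparison. A stop does shorten active stimulation while hardly changing sham, but that is true of any safety stop and does not come from these wording conflicts. How a shortened session is analysed can be left to the statistical analysis plan.

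**Conclusion.** The point holds as a minor safety-procedure inconsistency. One of three required ratings cannot be taken as scheduled: it falls about 5 minutes after the longest permitted stimulation. The two detailed lists share a single time point, and a third description differs from both. Discomfort short of pain has no consistent rule, and the consequence of a rating of 7 is worded in two ways. The timing result assumes the nominal 5-minute start and 10-minute spacing; the rest is a direct comparison of text.

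No effect on sample size, power or the efficacy analysis is shown. Nor do the documents support an estimate of how many sessions would be stopped. They give no rate for this trial. In one earlier protocol at the same university, 1 of 164 people asked to discontinue (1/164 = 0.6%). In another, 21 people completed the experiment without adverse events and with a median pain rating of 2. It is tempting to count every rating above 1 there as pain that would compel a stop. But the sensations reported were itching, tingling, prickling or mild heat, and the scale ran to extreme pain, so those ratings do not transfer to this trial's rule.

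**What to change.** 1. Put one schedule in Section 7, in the opening paragraph of the Section 12 plan and in Section 12, II. It should fit within 20 minutes and cover both onset and the later period: for example a rating before stimulation, ratings at 1, 5 and 15 minutes after the start, and one afterwards timed from the end of stimulation. If a session is set shorter than 20 minutes, place the last in-session rating before the current ends.
2. State one rule for discomfort short of pain (stop, adjust the electrodes, or experimenter's judgement) and use it in Section 7 and throughout Section 12. Which rule stands is a clinical choice for the sponsor.
3. Make stopping for pain compulsory in the opening paragraph of the Section 12 plan, as it already is elsewhere.
4. Use the same threshold (7 or higher) and the same words for what it ends in Section 7 and in Section 12, II.

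The cost is wording in two sections in one amendment. No visits are added, and the before and after ratings are already promised in Section 12.
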